6.4.4. Baseline Age and Other Age Definitions

Baseline age (in years) is the subject's enrollment age calculated as: $\text{FLOOR}([\text{date of informed consent} - \text{date of birth}] / 365.25)$, where $\text{FLOOR}()$ function returns the integer part of the result.

Age (years) at Pompe disease diagnosis is calculated as: $\text{FLOOR}([\text{date of Pompe disease diagnosis} - \text{date of birth}] / 365.25)$.

For subjects who are ERT-experienced (ie, subjects in Cohorts 1, 2, and 4), the age (years) at start of first ERT is calculated as: $\text{FLOOR}([\text{date of ERT initiation} - \text{date of birth} + 1] / 365.25)$.

6.4.5. Study Day (Relative Day)

The reference start day is defined for Cohort 1 and for Cohorts 2, 3, and 4 as follows:

- For Cohort 1: Visit 9 (Day 85 in Stage 2, Period 5) is considered the reference start day. This is the day of first dose of the 20 mg/kg ATB200 + 260 mg AT2221 co-administration.
- For Cohorts 2, 3, and 4: The study Day 1 in each cohort is the reference start day.

There will be no Day 0. If the date of interest occurs on or after the reference start day, then the relative study day is calculated as: $(\text{date of interest} - \text{date of reference start day} + 1)$.

Note: The appropriate reference start day should be used depending on whether the summary involves Cohort 1 or Cohorts 2, 3, and 4. For example, for Cohort 1, the relative day of the assessment at V12 will be calculated as: date of V12 – 85 + 1 (ie, Day 43).

If the date occurs before the reference start day, then study day is calculated as: $(\text{date of interest} - \text{date of reference start day})$. Thus, days before the reference start day will have a negative day displacement. For example, for Cohort 1, the relative day of the assessment at the efficacy baseline (V2) will be calculated as: date of baseline assessment – 85.

6.5. Analysis Visit Windows

Analysis visit windows will be used for the per-visit analyses.

6.5.1. Visit Windows for Cohort 1 Data

For the analysis of Cohort 1 data (both safety and efficacy), the visit windows in [Table 4](#) will be used. A general formula for deriving the visit windows is given in the footnotes. A summary at the last assessed value (LAV) will be provided for the efficacy analyses.

Table 4: Visit Windows for Analysis of Cohort 1 Safety, Efficacy, and Pharmacodynamic Data

	Days Based on the Original Study Reference Start Day (Visit 2)	Analysis Visit Windows	Days Based on the Re-scaled Reference Start Day (Visit 9)	Analysis Visit Windows
Visit Name	Target Day ^a		Target Day ^b	
Baseline ^c	1	See Section 6.4.1	1	See Section 6.4.5
Visit 10	99	Day 93 – 106	15	Day 9 – 22
Visit 11	113	Day 107 – 120	29	Day 23 – 36
Visit 12	127	Day 121 – 172	43	Day 37 – 88
Month 3	217	Day 173 – 262	133	Day 89 – 178
Month 6	307	Day 263 – 352	223	Day 179 – 268
Month 9	397	Day 353 – 442	313	Day 269 – 358
Month 12	487	Day 443 – 532	403	Day 359 – 448
Month 15	577	Day 533 – 622	493	Day 449 – 538
Month 18	667	Day 623 – 712	583	Day 539 – 628
Month 21	757	Day 713 – 802	673	Day 629 – 718
Month 24	847	Day 803 – 937	763	Day 719 – 853
Month 30	1027	Day 938 – 1117	943	Day 854 – 1033
Month 36	1207	Day 1118 – 1297	1123	Day 1034 – 1213
Month 42	1387	Day 1298 – 1477	1303	Day 1214 – 1393
Month 48	1567	Day 1478 – 1657	1483	Day 1394 – 1573
Month 54	1747	Day 1658 – 1837	1663	Day 1574 – 1753
Month 60	1927	Day 1838 – 2017	1843	Day 1754 – 1933
Month X ^d	T _{MONTH X}	d1 – d2	T _{MONTH X}	d3 – d4
LAV ^e	Target day corresponding to the LAV	Visit window corresponding to the LAV	Target day corresponding to the LAV	Visit window corresponding to the LAV

Abbreviations: LAV = last assessed value; PRO = patient-reported outcome; V = visit

Note: Analysis visit windows have been presented based on both the original study reference day (as per the Study Data Tabulation Model [SDTM] datasets) and the re-scaled referenced start day (to create the Analysis Data Model [ADaMs] datasets).

^a Cohort 1 target day starting from V2. Cohort 1 visits in Stages 3 and 4 designated as ‘Month 3,’ ‘Month 6,’ etc, are designed to ensure alignment with similarly labeled visits in Cohorts 2, 3, and 4 in order to facilitate by-visit comparisons among the cohorts. However, the target day corresponding to a Cohort 1 visit at Month X occurs at approximately (X * 30) days after Visit 12 (Day 127). For example, the target day for Month 3 is approximately at Day 3 * 30 + 127 = 217.

^b Cohort 1 target day for Month X (starting from V9) is determined as (X * 30) + 43. For example, the target day for Month 3 is approximately at Day 3 * 30 + 43 = 133.

^c For safety analysis by visit, baseline is taken from Visit 9 (Day 85), but for efficacy, biomarker, and PRO analyses, baseline value is taken from Visit 2 (Day 1). See Section 6.4.1 and Section 6.4.5.

^d Tx is the target day of planned assessment visit at Month X.

- If the derivation starts from the original study day at V2, then: T_{MONTH X} = (30 * X + 127). For example, the target day at Month 54 = T_{MONTH 54} = 30 * 54 + 127 = 1747. Target day of the assessment visit immediately before Month X is given by T_{BEFORE}. For example, T_{BEFORE} = T₄₈ = (30 * 48 + 127) = 1567. Target day of the assessment visit immediately after Month X is given by T_{AFTER} = T₆₀ = (30 * 60 + 127) = 1927. The visit windows are then given as d1 – d2, where d1 = ([T_{BEFORE} + T_{MONTH X}] / 2) + 1 and d2 = (T_{MONTH X} + T_{AFTER}) / 2.
- If the derivation starts from Visit 9, then target day at Month X is given by T_{MONTH X} = (30 * X + 43). For example, the target day at Month 54 is T_{MONTH 54} = 30 * 54 + 43 = 1663. Target day of the assessment visit immediately before Month X is given by T_{BEFORE}. For example, T_{BEFORE} = T₄₈ = (30 * 48 + 43) = 1483. Target day of the assessment visit immediately after Month X is given by T_{AFTER} = T₆₀ = (30 * 60 + 43) = 1843. Visit windows are given as d3 – d4, where d3 = ([T_{BEFORE} + T_{MONTH X}] / 2) + 1 and d4 = (T_{MONTH X} + T_{AFTER}) / 2.

^e LAV represents the result obtained from the subject’s last visit of assessment. Summary at the LAV will only be provided for the efficacy analyses.

Efficacy data will be summarized at: Baseline (Visit 2), Visit 12, Month 3, Month 6, Month 9, Month 12, Month 15, Month 18, Month 21, Month 24, and every 6 months thereafter in Stage 4. Safety data will be summarized at: Baseline (Visit 9), Visit 10, Visit 11, Visit 12, Month 3, Month 6, Month 9, Month 12, Month 15, Month 18, Month 21, Month 24, and every 6 months thereafter in Stage 4.

6.5.2. Visit Windows for Cohorts 2, 3, and 4 Data

For Cohorts 2, 3, and 4, the visit windows in [Table 5](#) will be used for analyses of safety and PD markers, and [Table 6](#) for the efficacy data.

Table 5: Visit Windows for Analyses of Cohorts 2, 3, and 4 Safety and Pharmacodynamic Data

Visit Name	Target Day	Visit Windows
Baseline	NA	Baseline is Visit 2
Day 1	1	Day 1 is Visit 3
Week 2	15	Day 2 – 22
Week 4	29	Day 23 – 60
Month 3	91	Day 61 – 136
Month 6	181	Day 137 – 226
Month 9	271	Day 227 – 316
Month 12	361	Day 317 – 406
Month 15	451	Day 407 – 496
Month 18	541	Day 497 – 586
Month 21	631	Day 587 – 676
Month 24	721	Day 677 – 811
Month 30	901	Day 812 – 991
Month 36	1081	Day 992 – 1171
Month 42	1261	Day 1172 – 1351
Month 48	1441	Day 1352 – 1531
Month 54	1621	Day 1532 – 1711
Month 60	1801	Day 1712 – 1891
Month X ^a	T _{MONTH X}	d1 – d2

Abbreviation: NA = not applicable

^a Target day of planned assessment visit at Month X is denoted T_{MONTH X} and it is given by T_{MONTH X} = (30 * X + 1). For example, the target day at Month 54 = T_{MONTH 54} = 30 * 54 + 1 = 1621. Target day of assessment visit immediately before Month X is given by T_{BEFORE}. For example, T_{BEFORE} = T₄₈ = (30 * 48 + 1) = 1441. Target day of assessment visit immediately after Month X is given by T_{AFTER}. For example, T_{AFTER} = T₆₀ = (30 * 60 + 1) = 1801. The visit windows are then given as d1 – d2, where d1 = ([T_{BEFORE} + T_{MONTH X}] / 2) + 1 and d2 = (T_{MONTH X} + T_{AFTER}) / 2.

Table 6: Visit Windows for Analyses of Cohorts 2, 3, and 4 Efficacy Data

Visit Name	Target Day	Visit Windows
Baseline	NA	NA (Baseline is Visit 2)
Month 3	91	Day 61 – 136
Month 6	181	Day 137 – 226
Month 9	271	Day 227 – 316
Month 12	361	Day 317 – 406
Month 15	451	Day 407 – 496
Month 18	541	Day 497 – 586
Month 21	631	Day 587 – 676
Month 24	721	Day 677 – 811
Month 30	901	Day 812 – 991
Month 36	1081	Day 992 – 1171
Month 42	1261	Day 11872 – 1351
Month 48	1441	Day 1352 – 1531
Month 54	1621	Day 1532 – 1711
Month 60	1801	Day 1712 – 1891
Month X ^a	T _{MONTH X}	d1 – d2
LAV	Target day corresponding to the LAV	Visit window corresponding to the LAV

Abbreviations: LAV = last assessed value; NA = not applicable

^a Target day of planned assessment visit at Month X is denoted T_{MONTH X} and it is given by T_{MONTH X} = (30 * X + 1). For example, the target day at Month 54 = T_{MONTH 54} = 30 * 54 + 1 = 1621. Target day of assessment visit immediately before Month X is given by T_{BEFORE}. For example, T_{BEFORE} = T₄₈ = (30 * 48 + 1) = 1441. Target day of assessment visit immediately after Month X is given by T_{AFTER}. For example, T_{AFTER} = T₆₀ = (30 * 60 + 1) = 1801. The visit windows are then given as d1 – d2, where d1 = ([T_{BEFORE} + T_{MONTH X}] / 2) + 1 and d2 = (T_{MONTH X} + T_{AFTER}) / 2.

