9. EFFICACY EVALUATION

9.1. Statement of the Null and Alternative Hypotheses

No hypothesis testing was planned for this study.

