9.4. Analysis of Efficacy Variables

All efficacy analyses will be conducted on the Efficacy population using the summary statistics defined in Section 6.2.1 and presented as described in Section 6.2.2.4. By-visit summaries will be based on the analysis visit windows defined in Section 6.5, which includes summary at baseline, every 3 months in Stage 3, and every 6 months in Stage 4. All efficacy data will be listed in subject-level data listings. See [Appendix 1](#) for the description of the endpoints as well as the derivation of the % predicted 6MWD, % predicted MIP, % predicted MEP, % predicted SNIP, and the total scores for the FSS, RHS, MMT, R-PAct, GSGC, and the PROMIS scales.

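### SAP Table 6 prints an impossible Month 42 efficacy window for Cohorts 2, 3 and 4 (lower bound 11872, upper bound 1351); the lower bound should read 1172

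*SAP*

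**What the plan says.** SAP Section 6.5.2 gives two window tables for Cohorts 2, 3 and 4. Table 5 covers safety and pharmacodynamic markers; Table 6 covers efficacy. In Table 6 the Month 42 row has target day 1261 and the window "Day 11872 – 1351".

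Footnote a to Table 6 explains how windows are built. The target day for Month X is 30 times X plus 1, and the bounds follow the rule "where d1 = ([T_{BEFORE} + T_{MONTH X}] / 2) + 1 and d2 = (T_{MONTH X} + T_{AFTER}) / 2".

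Table 6 is an operative rule. Section 9.4 states: "By-visit summaries will be based on the analysis visit windows defined in Section 6.5". Section 6.2.2.4 then presents the results in columns for Cohorts 1, 3 and 4, for Cohorts 1+4 pooled, and for Cohorts 1+3+4 pooled. Cohort 2 is shown separately.

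**The concern.** A window whose first day comes after its last day can hold no assessment. The SAP has no rule that would rescue an unassigned value. Section 6.6 only chooses among values already inside the same window, and Section 9.7 bases the analysis on observed values. If the row were coded literally, the Month 42 by-visit efficacy summary would have no data from the three cohorts that use Table 6. These have a planned total of 15 to 19 subjects (4–6, 5 and 6–8; SAP Section 5.1). Cohort 1 takes its windows from Table 4, so it would be the only contributor to two columns labelled as pooled.

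**Working it through.** **Inputs.** All come from SAP Section 6.5.2: the printed target days and windows in Tables 5 and 6, and the formula in footnote a to Table 6. With T(X) = 30X + 1, the lower bound is d1 = (T_before + T_X)/2 + 1 and the upper bound is d2 = (T_X + T_after)/2.

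**Step 1: does the formula reproduce the plan's other rows?** It does. Around the row in question:

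| Month | Target day | d1 by formula | d2 by formula | Table 6 prints |
|---|---|---|---|---|
| 30 | 901 | (721+901)/2+1 = 812 | (901+1081)/2 = 991 | 812 to 991 |
| 36 | 1081 | (901+1081)/2+1 = 992 | (1081+1261)/2 = 1171 | 992 to 1171 |
| **42** | **1261** | **(1081+1261)/2+1 = 1172** | **(1261+1441)/2 = 1351** | **11872 to 1351** |
| 48 | 1441 | (1261+1441)/2+1 = 1352 | (1441+1621)/2 = 1531 | 1352 to 1531 |
| 54 | 1621 | (1441+1621)/2+1 = 1532 | (1621+1801)/2 = 1711 | 1532 to 1711 |

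Of the 14 monthly rows in Table 6, 13 reproduce exactly. Two end rows need an input from outside the table. Month 3 needs the Week 4 target day from Table 5: (29 + 91)/2 + 1 = 61. Month 60 needs the next 6-monthly target: T(66) = 1981, so (1801 + 1981)/2 = 1891. Month 42 is the only failure, and only in its lower bound.

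**Step 2: how many days does the row hold?** As printed, 11872 exceeds 1351, so it holds 0 days. With the computed bound it holds 1351 − 1172 + 1 = 180 days.

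**Step 3: do other parts of the SAP agree on 1172?** Table 5 prints 1172 to 1351 for the same cohorts, visit and target day. In Table 6, Month 36 ends on Day 1171 and Month 48 starts on Day 1352, which leaves 1172 to 1351.

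**Step 4: what would literal coding affect?**
- By-visit efficacy summaries at Month 42: empty for Cohorts 3 and 4 on all efficacy measures. They would also be empty for Cohort 2 on the measures it has: upper-limb strength, pulmonary function, patient-reported outcomes and global impression (SAP Sections 4.4 and 9.4.1 to 9.6). Motor function is summarised only for Cohorts 1, 3 and 4.
- Pooled 1+4 and 1+3+4 columns at Month 42: Cohort 1 only.
- Not affected: Cohort 1 (Table 4), safety and pharmacodynamic summaries (Table 5), and subject-level listings (Section 9.4). The last-assessed-value summary is also unaffected, because footnote e to Table 4 defines it as the result from the subject's last assessment visit.

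**The case against.** The strongest reply is that this is a self-revealing typing error. The footnote formula, Table 5 and the neighbouring rows all fix the lower bound at 1172, so the analyst has no choice to make and there is no route to bias. A programmer who derives windows from the footnote, or who notices that the interval runs backwards, will arrive at 1172. That stands, and it is why the point is minor.

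A reader might infer that every Month 42 efficacy result in three cohorts will be lost. The documents do not support that. The loss arises only if the printed bound is coded literally, and even then it is confined to one by-visit row, since the listings and last-assessed values keep the data.

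A reader might also infer that the pooled columns would change composition unnoticed. They would not. Section 6.2.2.4 puts the Cohort 3 and Cohort 4 columns in the same display, and Section 6.2.1 requires the number of subjects in each continuous summary. The gap would be visible beside the Month 36 and Month 48 rows.

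Nor does any inference depend on the row. SAP Section 9.1 says "No hypothesis testing was planned for this study", and the SAP gives Month 42 no special role among the 6-monthly visits.

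None of this makes the printed rule correct. The cell stands in the table that governs the efficacy summaries.

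**Conclusion.** The Month 42 window in Table 6 is wrong as printed, by the SAP's own formula. The error is one lower bound (11872 in place of 1172) in 1 of 14 monthly rows. The correct window is Day 1172 to 1351, or 180 days.

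The consequence is conditional on literal programming. It would be limited to the Month 42 by-visit efficacy summaries for Cohorts 2, 3 and 4 and the two pooled columns that draw on Cohorts 3 and 4. How many subjects have an assessment in those 180 days is not stated, so the number affected can be bounded only by the planned 15 to 19.

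Two assumptions apply. The SAP file must show the same digits as the text quoted here; a stray digit from text extraction cannot be fully excluded, although the neighbouring cells read cleanly. The last assessed value must be taken from the last assessment visit, as footnote e to Table 4 defines it, and not only from records already placed in a Table 6 window. Severity is minor.

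**What to change.** In SAP Table 6, change the Month 42 lower bound from 11872 to 1172, so that the row reads Day 1172 to 1351. Then check that the programmed windows for Cohorts 2, 3 and 4 are contiguous and do not overlap.

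Replacing the whole table with the footnote formula is not needed and would not work for Table 6 alone. Its first visit, Month 3, is preceded by Baseline, which has no target day, so the lower bound there cannot be computed without borrowing Week 4 from Table 5.

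The cost is one figure in the SAP and a short programming check. Design, conduct and data collection are unaffected.

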6.6. Multiple Assessments in a Visit Window

Data from both scheduled and unscheduled visits as well as early termination (ET) visits that are within 30 days of the last ATB200 infusion visit will be considered in determining values for specified visit windows. Assessments from ET visits that are more than 30 days from the last ATB200 infusion will not be used.

No rules will be implemented for reassigning/remapping missing visits due to COVID-19 related reasons to address delayed visits.

If multiple assessments (eg, from scheduled and unscheduled visits, as well as ET visits that are within 30 days of the last ATB200 infusion visit) occur in the same visit window, the value closest to the planned target visit day will be used for that visit. If 2 values are equidistant from the target day or occur on the same day but at different times, the last assessment in

chronological order will be used. If the 2 assessments have the same date and time, then the average value will be used.

6.7. Completion of Study

The Study Completion page in the eCRF was designed to cover the entire study duration so that an answer of “Yes” to the question “Did the subject complete the study?” defines a completer for the study. It is checked “No” for subjects who withdraw from the study, and the checkbox is expected to remain blank for subjects who are ongoing in the study. Therefore, in order to determine the study completion/discontinuation during different stages of the study, the study dose administration records and the duration of exposure should be used together to make that determination.

Unless otherwise stated, completion during the 4 stages of the study is defined as follows:

- Stage 1 completers refer to the Cohort 1 subjects who completed Stage 1 of the study.
- Stage 2 completers refer to the Cohort 1 subjects who completed Stage 2 of the study.
- Stage 3 completers include all subjects who completed Stage 3 (24 months treatment with 20 mg/kg ATB200 + 260 mg AT2221 co-administration).
- Stage 4 completers (ie, also referred to as ‘study completers’) include all subjects who continued in the study until they transitioned to commercial product or until study closeout by the sponsor during Stage 4.

Note: The plan is to consider those subjects who were moved into an ongoing EAP study due to unavailability of commercial product in their home countries as study completers.

The study completion summary will be included in the overall disposition summary table.

7. STUDY POPULATION

7.1. Subject Disposition

The count and percentage of subjects who entered, who completed, or who discontinued prematurely from the study during Stage 1, Stage 2, Stage 3, and Stage 4 and the reasons for discontinuation will be presented. The summary will be conducted on the All Enrolled Subjects population and will include:

- Number of subjects who entered Stage 1 and the number of subjects who completed Stage 1 (presented by SAD treatment dose)

- Number of subjects who entered Stage 2 and the number of subjects who completed Stage 2 (presented by MAD treatment dose)

Note: The summaries for the above items were previously reported in iCSR-1 and will not be repeated in this SAP, as the data are not expected to change. For the final CSR, the plan is to copy the pertinent summaries from iCSR-1.

- Number of subjects who entered Stage 3 (presented by cohort, including the total):

- Number of subjects who completed Stage 3

- Number of subjects who discontinued study prematurely in Stage 3

- Reasons for discontinuation during Stage 3

- Number of subjects who entered Stage 4 (presented by cohort, including the total):

- Number of subjects who completed Stage 4 (ie, study completers)

- Number of subjects who discontinued study prematurely in Stage 4

- Reasons for discontinuation during Stage 4

- Overall number of subjects who completed the study:

Note: This is based on the checkboxes marked “Yes” in the study completion page of the eCRF, and it should be equal to the number of Stage 4 completers.

- Overall number of subjects who discontinued study prematurely

- Reasons for study discontinuation overall

A listing of all disposition data will be provided in subject-level data listings. There will be no separate listings by stage.

7.2. Screened Subjects and Screen Failures

The number of subjects screened and the number who passed/failed screening will be presented overall in a single column (ie, the total column) in the disposition table. Demographic data for screen failures will be provided in individual subject-level data listings.

7.3. Protocol Deviations

Protocol deviation data are collected from the clinical research associates' monitoring reports and consolidated into a deviation log at PRA International (now ICON), and then transferred to Amicus for review on an ongoing basis. According to the protocol deviation plan for the study, deviations are classified as either important or not important. Important protocol deviations will be summarized cumulatively across all study stages by deviation type, based on the All Enrolled Subjects population using the methodology described in Section 6.2.1, and presented by cohort as outlined in Section 6.2.2.2. A subject-level data listing of all protocol deviations will be provided showing, among other items, the cohort in which the subject belongs, deviation type/code, deviation date, deviation description, and whether or not the deviation was classified as an important deviation (Y/N).

7.4. Demographic and Baseline Characteristics

The baseline and demographic characteristics and other related baseline information will be summarized on the All Enrolled Subjects population using the methodology described in Section 6.2.1 and presented by cohort as outlined in Section 6.2.2.1. A listing of all baseline information will be provided. Demographic and baseline characteristics to be presented in the summary table include:

- Age (at informed consent date in years), both as a continuous parameter and by categories of 18 to 64, and ≥ 65
- Sex
- Race
- Ethnicity (for sites in US only)
- Height (cm)
- Weight (kg)
- Body mass index (BMI) (kg/m^2). BMI will be calculated as body weight (kg)/body height² (m^2).

The following Pompe disease history information will be summarized with descriptive statistics for the All Enrolled Subjects population.

- Number and percentage of subjects with more than 2 years of experience of ERT (Y/N)
- Frequency of ERT infusion
- Dose of ERT
- Duration of ERT infusion

The following information related to falls history will be summarized with descriptive statistics for the All Enrolled Subjects population:

- Number of falls in the past 30 days (prior to enrollment date)
- Number of falls in the past 1 year (prior to enrollment date)
- Change in the rate of falling in the past 1 year (decreased, no change, increased)

7.5. Listing of Subjects' Inclusion and Exclusion Criteria

A listing of subjects' inclusion and exclusion criteria will be provided showing which specific eligibility criteria were met/not met.

